^l All patients will receive infusions of either ALVR105 or placebo. Patients will receive the same [REDACTED] dose for patients ≤ 40 kg or [REDACTED] dose for patients > 40 kg for all infusions of ALVR105, administered at a dose interval of every 14 days (± 3 days). Placebo infusions will be administered every other week in order to maintain the blind. As GVHD and CRS are a theoretical safety concern associated with administration of third-party allogeneic T cells, the incidence and severity of GVHD and CRS will be monitored during the study. No patients will be permitted to receive a subsequent infusion of ALVR105 if they develop new onset GVHD Grade > 2 or worsening of GVHD (ie, relative to baseline GVHD at the time of enrollment into the study) at the proposed time for infusion of the next dose, or if they develop CRS Grade > 2 ; if any patient develops GVHD or CRS, the Medical Monitor should be contacted immediately, and the patient treated per standard of care. If discontinued for CRS or GVHD these participants should be followed up to resolution of symptoms. Patients may resume treatment only with consultation and agreement between the Medical Monitor and the Investigator. If possible, IVIG and ALVR105 should not be administered on the same day.

^m Patients will be monitored closely and must remain in the clinic for ≥ 1 hour after the end of each infusion. Vital signs, including body temperature, heart rate, O_2 saturation, respiration rate, and blood pressure, will be measured at the end of the infusion, and at 15, 30, 45, and 60 minutes after the end of the infusion. Patients must also remain on continuous pulse oximetry for ≥ 30 minutes after the end of the infusion. Post-infusion monitoring should be completed for all infusions of study treatment.

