^aThe infection assessment will be performed for all patients who require either treatment for disease or initiation of preemptive therapy during both the primary study period and the follow-up period through Week 26 (Section 8.3). It is very important to ensure that all procedures, as outlined in the SoA, are performed immediately prior to the initiation of treatment of viral diseases or initiation of preemptive therapy (ie, on the day anti-viral therapy is initiated). Most importantly, a plasma sample for AdV, BKV, CMV, HHV-6, and JCV and a PBMC sample for EBV for PCR testing at the central laboratory should be collected. Patients who develop viral infections will continue to be followed in the study and complete all remaining visits through Week 26.

^oAssessment of quality of life (using FACT-BMT, EQ-5D-5L, EQ-5D-Y, EQ-5D-Y Proxy Version 1questionnaires, as age-appropriate) should be completed prior to any study procedures at this visit.

Table 4: Schedule of Activities: Short-Term Follow-Up--Period 2, All Ages (Weeks 18 to 26, All Cohorts)

Study Week	Week 18	Week 22	Week 26/ET ^a
Study Day	126	154	182
Visit Window (Days)	±3	±3	±3
Study Procedures			
Prior & concomitant medications	X	X	X
Adverse events ^b	X	X	X
Weight			X
Vital signs	X	X	X
12-lead ECG			X
Clinical Labs			X
BKV, AdV, CMV, JCV, and HHV-6 viral load ^c		X	X
EBV PCMBs ^d		X	
Virus-Specific T Cell assessment ^e	X	X	X
Infection assessment ^f	X	X	X
Quality of Life (FACT-BMT and EQ-5D-5L, EQ-5D-Y, EQ-5D-Y Proxy Version 1) ^g	X	X	X

Abbreviations: AdV = adenovirus; ALT = alanine aminotransferase; AST = aspartate aminotransferase; BKV = BK virus; CBC = complete blood count; CMV = cytomegalovirus; EBV = Epstein-Barr virus; ECG = electrocardiogram; ET = Early Termination Visit; GVHD = graft versus host disease; HHV-6 = human herpesvirus 6; JCV = JC virus; LFT = liver function test; PBMCs = peripheral blood mononuclear cells

Note: Visits may be done via a home health visit as agreed with the Sponsor. Please see the Study Manual for more information.

^aThe Early Termination Visit will be performed for all patients who are prematurely discontinued from the study up to Week 26. It is very important to ensure that all procedures are performed in such patients at this visit prior to discontinuing the patient from the trial. Most importantly, a plasma sample for AdV, BKV, CMV, HHV-6, and JCV and a PCMB sample for EBV for PCR testing at the central laboratory should be collected at this visit.

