2.2.2. Overview of Clinical Studies with Virus-Specific T Cells

2.2.2.1. Results of the CHARMS Study with Third Party-Derived Multivirus-Specific T Cells, ALVR105

To investigate the safety and clinical efficacy of ALVR105, a multivirus-specific T cell product reactive for BKV, AdV, HHV-6, EBV, and CMV generated from third-party, healthy, eligible donors, a Phase 1/2a clinical study was conducted in recipients of allogeneic HCT with drug-refractory infections with ≥ 1 of the 5 viruses targeted by ALVR105 (Tzannou, 2017). In this study, patients received a single IV infusion of 2×10^7 partially HLA-matched ALVR105 cells/m², with the option to receive a second infusion after 4 weeks (actual range 14 days to >6 weeks) and additional infusions at biweekly intervals thereafter. Therapy with standard antiviral medications could be continued at the discretion of the treating physician (Tzannou, 2017).

A total of 58 patients with drug-refractory infections following allogeneic HCT were infused with ALVR105 cell lines matched at 1 to 6 HLA antigens; 54 of these patients completed study treatment and the initial 28-day safety follow-up (the first 38 patients to complete the study are reported in Tzannou et al, 2017. Of the 71 total infections treated, 25 (35.2%) infections were BKV and 24 (33.8%) infections were CMV. Of the 58 patients who were treated (one of whom had 2 courses of treatment), 48 patients were treated for a single virus, 10 patients were treated for 2 viral infections, and 1 patient was treated for infections by 3 different viruses.

All infusions were well tolerated. None of the patients developed cytokine release syndrome (CRS). In the weeks after infusion, 1 patient developed recurrent Grade 3 gastrointestinal (GI) GVHD following rapid systemic corticosteroid taper, and 8 patients developed recurrent ($n = 4$) or de novo ($n = 4$) Grade 1 to 2 skin GVHD, which resolved with the administration of topical treatments ($n = 7$) and reinitiation of systemic corticosteroids after taper ($n = 1$). Between 3 and 6 months after infusion, 2 patients experienced a flare of upper GI GVHD, which resolved after a brief systemic corticosteroid course.

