5.2. Exclusion Criteria

Patients who meet any of the following criteria will be excluded from participation in the study:

Medical Conditions

1. Has a history of AdV, BKV, CMV, EBV, HHV-6, and/or JCV end-organ disease within 6 months prior to treatment assignment
2. Has evidence of AdV, BKV, CMV, EBV, HHV-6, and/or JCV viremia for more than 3 viruses, from a central or local laboratory at any time during Screening prior to treatment assignment
3. Evidence of active Grade >2 acute GVHD (for additional information on acute GVHD grading and severity, see Appendix 5 [[Section 10.5](#)] or CRS Appendix 6 [[Section 10.6](#)], respectively).
4. Presence of non-minor uncontrolled or progressive bacterial or fungal infections (ie, evidence of bacteremia, fungemia, disseminated, and/or organ-specific infection not well controlled by present therapies)
5. Presence of progressive, uncontrolled viral infections with evidence of end organ disease
6. Known history or current (suspected) diagnosis requiring treatment of CRS associated with the administration of peptides, proteins, and/or antibodies
7. Evidence of encephalopathy at screening
8. Relapse of primary malignancy other than minimal residual disease.

Prior/Concomitant Therapy

9. Donor lymphocyte infusion performed within 21 days prior to randomization
10. Received within 7 days prior to treatment assignment any of the following: ganciclovir, valganciclovir, foscarnet, acyclovir (at doses >3200 mg PO per day or >25 mg/kg IV per day), valacyclovir (at doses >3000 mg PO per day), famciclovir (at doses >1500 mg PO per day)
11. Received any investigational antiviral agent/biologic therapy within 30 days prior to screening or plans to receive during the study any of the following: cidofovir, CMV hyper-immune globulin, or any investigational CMV antiviral agent/biologic therapy.
12. Ongoing therapy with high-dose systemic corticosteroids (ie, prednisone equivalent dose >0.5 mg/kg/day) within 7 days prior to screening
13. Prior therapy with antithymocyte globulin, alemtuzumab (Campath-1H), or other immunosuppressive T cell-targeted monoclonal antibodies within 28 days of treatment assignment
14. Receipt of mechanical ventilation of any type, within 1 month prior to the administration of ALVR105 (unless related to airway control)
15. Undergoing dialysis at any time during the screening period

Prior/Concurrent Clinical Study Experience

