3.3 Patient Data and Study Conduct

3.3.1 *Patient Disposition*

Patient disposition information will be summarized using the Enrolled Population. The numbers and percentages of patients who were screened, screen failure along with the reasons of screen failure, not dosed, dosed, completed study drug, discontinued study drug early along with the reasons for early discontinuation of study drug, completed the study, and discontinued the study early along with the reasons for early discontinuation of study, received a Week 52 follow-up call will be summarized.

The numbers and percentages of patients in Safety Population with reason for exclusion will also be summarized.

By-patient listings will also be provided for patient disposition, screen failures, patients who were enrolled but not dosed, and reason for exclusion from analysis population.

3.3.2 *Protocol Deviations*

The numbers and percentages of patients with protocol deviations by deviation category will be summarized on Safety Population. All protocol deviations will be determined prior to database lock and listed by patient.

3.3.3 *Demographic and Baseline Characteristics*

Demographic (age, sex, race, and ethnicity) and baseline characteristics (height, weight, BMI, and childbearing potential at baseline) will be summarized with descriptive statistics or counts and percentages of patients as appropriate for safety population.

The following disease characteristics will also be summarized using frequencies and percentages: diagnosis, donor type, HLA alleles from the study patient, the allogeneic HCT donor(s), and the VST donor(s) as well as the number of shared alleles among these individuals, pre-conditioning therapy received, CMV serostatus at baseline of donor and recipient, letermovir use at Baseline, presence of Baseline viremia (based on central lab) and level of conditioning (myeloablative, reduced intensity, and non-myeloablative). A by-patient listing will be provided.

3.3.4 *Medical History*

Medical history will be coded to system organ class and preferred term using the Medical Dictionary for Regulatory Activities (MedDRA). The numbers and percentages of patients with

medical history by system organ class and preferred term will be summarized for safety population.

A by-patient listing of medical history will be provided.

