3.5.1 Adverse Events (AEs)

All AEs will be coded to system organ class and preferred term using MedDRA. Treatment emergent adverse events (TEAEs) are defined as an AE with onset or worsening on or after the first dose of study treatment through the end of study (i.e., Week 26).

An overall summary of AEs will be provided with the number and percentage of patients who experienced at least 1 AE or TEAE in the following categories:

- Any TEAEs
- Any TEAEs by severity
- Any treatment-related TEAEs
- Any AEs of special interest (AESIs)
- Any treatment-emergent AESI (TEAESIs)
- Any treatment-related TEEAESIs
- Any serious AEs (SAEs)
- Any treatment-emergent serious AEs (TESAEs)
- Any treatment-related TESAEs
- Any TEAEs leading to discontinuation of study treatment
- Any TEAEs leading to discontinuation of study
- Any AEs leading to death

The numbers and percentages of patients will also be presented by system organ class (SOC) and preferred term (PT) for each of the TEAE categories in the summary. Patients with multiple AEs will be counted only once per SOC and PT. The number and percentage of patients with TEAEs will be tabulated by PT and by the highest CTCAE Grade.

Listings will be presented specifically for any AEs, deaths, SAEs, and TEAEs leading to discontinuation of study treatment and study.

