3.5.2 AEs of Special Interest

Adverse events of special interest (AESI) include infusion-related AEs, GVHD, and cytokine release syndrome (CRS). These AESIs will be reviewed by the DSMB as per the DSMB Charter. Criteria for acute and chronic GVHD and CRS can be found in Protocol Appendix 5 and 6, respectively. The number and percentage of patients who had the AESIs will be summarized:

- Severity and incidence of acute GVHD
- Severity and incidence of chronic GVHD
- Severity and incidence of CRS
- Severity and incidence of infusion-related AEs
- Severity and incidence of graft failure

Subgroup analyses may be conducted for the severity and incidence of acute GVHD by HLA type and the number of HLA matching.

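### SAP 3.5.2 gives one acute-GVHD percentage that mixes new onset with worsening of GVHD present at entry, and no physical examination is scheduled between Week 14 and Week 26

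*SAP*

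**What the plan says.** **Entry.** Protocol 5.2, criterion 3, excludes "Evidence of active Grade >2 acute GVHD", which leaves active Grade 1-2 disease eligible. The dosing footnote to Protocol Table 2 (repeated in the SAP's copy of the schedule) allows for this, because it withholds the next infusion for "worsening of GVHD (ie, relative to baseline GVHD at the time of enrollment into the study").

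**Analysis.** SAP 3.5.2 states that "The number and percentage of patients who had the AESIs will be summarized", with severity and incidence of acute GVHD as one item. The optional HLA subgroups are the only split: "Subgroup analyses may be conducted for the severity and incidence of acute GVHD by HLA type and the number of HLA matching". SAP 3.5.1 defines a treatment-emergent event as "an AE with onset or worsening on or after the first dose of study treatment through the end of study". It lists AESIs and treatment-emergent AESIs on separate lines, but 3.5.2 does not say which it summarises. The disease characteristics in SAP 3.3.3 end with "presence of Baseline viremia (based on central lab) and level of conditioning (myeloablative, reduced intensity, and non-myeloablative"); GVHD status is not among them. Protocol 9.4.5 promises exact binomial 95% confidence intervals for AESIs, including acute and chronic GVHD. SAP 3.5.2 does not mention them.

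**Follow-up.** Protocol 1.3, "Table 4: Schedule of Activities: Short-Term Follow-Up--Period 2, All Ages (Weeks 18 to 26, All Cohorts"), reproduced as SAP Table 8, has adverse-event collection at all three visits. It has no physical-examination row, and clinical labs appear at Week 26/ET only.

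**The concern.** Protocol 2.3.2 names GVHD as one of the main risks of this third-party T-cell product. The protocol uses GVHD status at entry to decide on further dosing, but the SAP does not use it in the analysis. A patient who develops GVHD for the first time and a patient whose Grade 1 skin disease becomes Grade 2 both add one to the same numerator, over a denominator that includes patients who already had the disease. A reader who wants the rate of new GVHD after infusion cannot get it from that table.

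Because 3.5.2 does not state a treatment-emergent limit, it is also open whether GVHD present before the first dose is counted. Protocol Table 1 documents adverse events from consent, while Protocol 8.5.1 sends events that start before treatment assignment to medical history.

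In follow-up, the completeness of GVHD counts rests on general adverse-event collection. Skin signs and bilirubin, both of which feed the Appendix 5 staging, are not scheduled at Weeks 18 and 22.

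**Working it through.** The plan states no GVHD rate, so there is no figure to reproduce. Three checks follow.

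**1. Is there really no split?** Taking the sections together: entry permits Grade 1-2 (Protocol 5.2); worsening is judged against baseline (Table 2 footnote l); treatment-emergent status merges onset and worsening (SAP 3.5.1); baseline GVHD is not tabulated as such (SAP 3.3.3); the only subgroups are by HLA (SAP 3.5.2). So the planned table does not separate the two kinds of event.

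The severity scale is also unclear. SAP 3.5.2 points to the criteria in Protocol Appendix 5, while Protocol 10.3.3 grades adverse events by CTCAE v5.0 and makes an exception only for CRS.

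**2. How far can pooling move the figure?** Let b be the share with active GVHD at first dose, n the new-onset risk in the others, and w the worsening risk in those with GVHD. Then

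pooled = b × w + (1 − b) × n.

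None of b, n or w is in the documents; the values below are assumptions.

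| b | n = 10%, w = 40% | ratio to n | n = 20%, w = 50% | ratio to n |
|---|---|---|---|---|
| 10% | 0.04 + 0.09 = 13% | 1.3 | 0.05 + 0.18 = 23% | 1.15 |
| 20% | 0.08 + 0.08 = 16% | 1.6 | 0.10 + 0.16 = 26% | 1.3 |
| 40% | 0.16 + 0.06 = 22% | 2.2 | 0.20 + 0.12 = 32% | 1.6 |

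For context, Protocol 2.2.2.1 reports early GVHD in the earlier study of this product by type. "1 patient developed recurrent Grade 3 gastrointestinal (GI) GVHD following rapid systemic corticosteroid taper", and 8 patients had skin GVHD, 4 recurrent and 4 de novo. That makes 1 + 4 = 5 recurrent and 4 de novo among 58 patients. With Clopper-Pearson 95% intervals:

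- all early cases: 9/58 = 15.5% (7.3 to 27.4)
- de novo: 4/58 = 6.9% (1.9 to 16.7)
- recurrent: 5/58 = 8.6% (2.9 to 19.0)

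The ratio of all to de novo is 9/4 = 2.25. The denominator is 58 throughout because the number with prior GVHD is not given.

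**3. What does the schedule leave uncovered?** The last scheduled physical examination is at Week 14 (Day 98) and the last visit is at Week 26 (Day 182): 182 − 98 = 84 days, and 84/182 = 46% of the study period. Clinical labs are scheduled at Days 98 and 182 but not at Days 126 and 154. SAP Appendix 1, Table 4, nevertheless has a Week 26 analysis window for physical-examination data. The earlier study reported 2 flares of upper GI GVHD 3 to 6 months after infusion, a period that overlaps this gap.

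**Precision.** At an assumed 20% incidence, the exact 95% interval for the whole cohort is 6.8 to 40.7% (5/25) up to 8.4 to 36.9% (7/35). With b = 20%, the active-GVHD group would hold 0.20 × 25 = 5 to 0.20 × 35 = 7 patients.

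**The case against.** The best defence is that this is a small, single-arm, descriptive cohort and that much is already in place. Counting onset or worsening is a conventional treatment-emergent definition, and stable GVHD from entry would not meet it. SAP 3.3.4 tabulates and lists medical history, and SAP 3.5.1 lists adverse events by patient, so in 25 to 35 patients the cases could be sorted by hand. That is largely true. It shows that the split is feasible; it does not supply a pre-specified table, denominators or baseline grades.

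Several stronger readings are tempting, and the documents do not support them.

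- **That GVHD is never staged.** Table 2 footnotes d and l call for a skin check without complaint and a GVHD judgement against baseline before further infusions, and clinical labs at infusion visits include bilirubin. What is missing is a dedicated schedule row for recording organ stage; the case report form is not available to check.
- **That follow-up cases surface only if the patient complains.** Staff ask open-ended questions (Protocol 8.5.2), review medical records at the next visit (10.3.1) and must follow participants proactively (8.5.3). None of this is GVHD-specific, but it is not unprompted reporting.
- **That the protocol's 6-week acute-GVHD window goes mostly unexamined.** That window, in Protocol 7.1 and 9.5.1.1, is a criterion for giving no further infusions. It does not define when GVHD is to be ascertained.
- **That 2.25 is the inflation to expect here.** It compares all with de novo cases in another study. The protocol does not say that the recurrent cases had active GVHD at infusion.
- **That acute GVHD is the main safety endpoint.** SAP 2.3.4 lists it first among unranked endpoints, and Protocol 2.3.2 names inflammation at disease sites beside it.

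**Conclusion.** The point holds as a reporting weakness that should be corrected. SAP 3.5.2 combines new-onset and worsening acute GVHD in one percentage, ignores baseline status and leaves the treatment-emergent limit unstated. The size is unknown because the share entering with GVHD is not in the documents. Under the assumed values the pooled figure is 1.15 to 2.2 times the new-onset risk; it would be close to 1 if few patients enter with GVHD or if the two risks are similar. The pooled percentage is a legitimate treatment-emergent summary, but it is not the rate of new disease.

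The follow-up gap is a limitation on completeness: 84 of 182 days without a scheduled physical examination, and no clinical labs between Weeks 14 and 26. The documents do not allow an estimate of how many cases could be missed.

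**What to change.** Change the SAP only, before the Phase 2 database lock.

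- **SAP 3.5.2.** State that the summary covers treatment-emergent acute GVHD. Keep the overall figure, and beside it report (a) new onset among patients with no current or prior acute GVHD at first dose, (b) recurrence among patients whose acute GVHD had resolved before first dose, and (c) worsening among patients with active acute GVHD at first dose. Give each its own denominator, the maximum Appendix 5 (MAGIC) grade where recorded, and the exact binomial 95% intervals promised in Protocol 9.4.5. Category (b) is needed because a two-way split has no place for GVHD that resolved and came back.
- **SAP 3.3.3.** Add baseline acute-GVHD status and grade, taken from eligibility and medical-history data where recorded.
- **Limitation.** State that no physical examination was scheduled after Week 14 and no clinical labs between Weeks 14 and 26, so GVHD in that period rests on general adverse-event questioning and record review.

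The cost is one extra table and one baseline line, with no new data collection. The downsides are small cells in 25 to 35 patients, wide intervals, and possibly incomplete baseline grades. Added visits or schedule rows are not an option for this cohort: SAP 1 says that its patients were already enrolled, treated and followed.

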3.5.3 Clinical Laboratory Tests

Laboratory assessments comprise safety laboratory tests (hematology, clinical chemistry and routine urinalysis), pregnancy test and other screening tests.

Descriptive statistics will be provided for safety laboratory test results and changes from baseline. A shift table, presenting the 2-way frequency tabulation for baseline and the worst post-baseline value according to the v5.0 NCI CTCAE grade, will be provided for safety laboratory tests.

Listings will be presented for all laboratory data and all test values outside the normal range will be flagged.

3.5.4 Vital Signs

Descriptive statistics will be provided for vital signs (including blood pressures, pulse rate, respiratory rate, oximetry, and body temperature), body weights, and BMIs by visit. Changes from baseline will also be summarized.

All vital sign data will be listed by patient.

3.5.5 Electrocardiograms

Electrocardiogram (ECG) measurements include heart rate (bpm) and measures PR (msec), QRS (msec), and QTc (msec) (corrected using Bazett's method, QTcB). Descriptive statistics will be provided for PR, QRS, and QTcB and the changes from baseline.

All ECG parameters and the Investigator interpretation of findings including details of any abnormalities will be listed by patient.

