8.4.2. Vital Signs

- Temperature, pulse rate, O₂ saturation, respiratory rate, and blood pressure will be assessed.
- Blood pressure and pulse measurements will be assessed with a completely automated device. Manual techniques will be used only if an automated device is not available.

- Vital signs will be measured in a semi-supine position after 5 minutes rest and will include temperature, systolic and diastolic blood pressure, and pulse and respiratory rate.

8.4.3. *Electrocardiograms*

- Single 12-lead electrocardiograms (ECG) will be obtained as outlined in the SoA (see [Section 1.3](#)) using an ECG machine that automatically calculates the heart rate and measures PR, QRS, QT, and QTc (corrected using Fredericia's and Bazett's methods) intervals.
- The ECG will be performed within 1 hour after study treatment administration on visits with administration of study therapy.

8.4.4. *Clinical Safety Laboratory Assessments*

- See Appendix 2 ([Section 10.2](#)) for the list of clinical laboratory tests to be performed and to the SoA ([Section 1.3](#)) for the timing and frequency.
- Samples will be sent to the appropriate central laboratory(ies) following the procedure(s) described in the lab manual.
- The Investigator must review the laboratory report, document this review, and record any clinically significant changes occurring during the study as an AE. The laboratory reports must be filed with the source documents.
- Abnormal laboratory findings associated with the underlying disease are not considered clinically significant unless judged by the Investigator to be more severe than expected for the participant's condition.
- All laboratory tests with values considered clinically significantly abnormal during participation in the study or within 28 days after the last dose of study intervention should be repeated until the values return to normal or baseline or are no longer considered clinically significant by the Investigator or Medical Monitor.
 - If clinically significant values do not return to normal/baseline within a period of time judged reasonable by the Investigator, the etiology should be identified, and the Sponsor notified.
 - All protocol-required laboratory tests, as defined in Appendix 2 ([Section 10.2](#)), must be conducted in accordance with the laboratory manual and the SoA ([Section 1.3](#)).

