9.4.5. Safety Analysis

All safety data will be summarized by cohort, stratum, [REDACTED] [REDACTED]. For Cohort OL, results will be presented by stratum and overall, as all patients in Cohort OL receive only ALVR105.. Categorical endpoints will be summarized using the number and percentage of patients within each category. Continuous endpoints will be summarized descriptively with summary statistics (number of non-missing observations, arithmetic mean, standard deviation, median, minimum, and maximum).

Adverse events will be coded using the Medical Dictionary for Regulatory Activities. A treatment emergent adverse event (TEAE) is defined as an AE with onset or worsening on or after the first dose of study treatment. TEAEs will be summarized by System Organ Class and Preferred Term and further by severity (according to the National Cancer Institute [NCI] Common Terminology Criteria for Adverse Events [CTCAE] v5.0) and by relationship to study treatment. The incidence of SAEs will be summarized.

The incidence of AEs of special interest (AESIs), including acute and chronic GVHD and CRS, and their corresponding exact binomial 95% confidence intervals will be presented.

Descriptive statistics will be provided for continuous clinical laboratory, vital sign, and ECG data for both the raw data and change from baseline. Abnormal laboratory results will be graded according to NCI CTCAE v5.0, if applicable. Shift tables, presenting the 2-way frequency tabulation for baseline and the worst post-baseline value according to the NCI CTCAE grade, will be provided for selected clinical laboratory tests.

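### SAP 3.5.5 summarises QTc by Bazett only, though the protocol has Fridericia measured too, so a heart-rate change can shift the QTc summary with no change in QTcF

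*SAP*

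**What the plan says.** Protocol 8.4.3 (Electrocardiograms) requires a machine that calculates heart rate and "measures PR, QRS, QT, and QTc (corrected using Fredericia's and Bazett's methods) intervals". On timing it says: "The ECG will be performed within 1 hour after study treatment administration on visits with administration of study therapy". Protocol 9.4.5 then promises summaries with no choice of correction: "Descriptive statistics will be provided for continuous clinical laboratory, vital sign, and ECG data for both the raw data and change from baseline".

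SAP 3.5.5 is narrower. It lists heart rate, PR, QRS and QTc ("corrected using Bazett's method, QTcB") as the ECG measurements, and the planned tables are narrower again: "Descriptive statistics will be provided for PR, QRS, and QTcB and the changes from baseline". QTcF, uncorrected QT and ECG heart rate are not summarised, and no reason is given. There are no QTc threshold or outlier categories. The section does add a listing: "All ECG parameters and the Investigator interpretation of findings including details of any abnormalities will be listed by patient".

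SAP 3.1.3 defines baseline as the last non-missing value before the first dose. Protocol Table 2 places the Day 1 ECG after the infusion, so the baseline ECG would normally be the screening one.

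**The concern.** The two corrections treat heart rate differently, so a table with only one of them mixes any change in repolarisation with any change in rate, as judged by the other. The schedule gives room for a change in rate. Baseline is normally a screening ECG, which may be taken at any time from the day of transplant. The comparison ECGs are mostly taken within an hour after an infusion, over 14 weeks of recovery.

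The SAP covers only the open-label cohort of 25 to 35 patients, all on ALVR105. In a randomised comparison, a rate-driven shift common to both arms would largely cancel. Here nothing cancels it. A reader of the QTcB table could take a rate effect for a drug effect, or miss a rise in QTcF offset by a falling rate.

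**Working it through.** The documents state no QT figure, so there is none to reproduce. The check is of how the two formulas relate.

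**Inputs.** The formulas are those named in Protocol 8.4.3. Heart rates of 50 to 120 bpm and a QTcF of 400 or 420 ms are assumptions; neither document gives observed or expected values.

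**Relation.** With RR = 60/HR in seconds, QTcB = QT/RR^(1/2) and QTcF = QT/RR^(1/3). Dividing, QT cancels:

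QTcB/QTcF = RR^(-1/6) = (HR/60)^(1/6).

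**Single readings.**

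| HR (bpm) | Ratio | QTcB if QTcF = 400 ms (gap) | QTcB if QTcF = 420 ms (gap) |
|---|---|---|---|
| 50 | 0.9701 | 388.0 (-12.0) | 407.4 (-12.6) |
| 60 | 1.0000 | 400.0 (0) | 420.0 (0) |
| 80 | 1.0491 | 419.6 (+19.6) | 440.6 (+20.6) |
| 100 | 1.0889 | 435.5 (+35.5) | 457.3 (+37.3) |
| 120 | 1.1225 | 449.0 (+49.0) | 471.4 (+51.4) |

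A direct check at 100 bpm: a QT of 354.2 ms with RR = 0.6 s gives QTcB = 457.3 ms and QTcF = 420.0 ms, as in the table.

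**Change from baseline with QTcF held constant.** The change in QTcB is QTcF x [(HR2/60)^(1/6) - (HR1/60)^(1/6)].

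- 80 to 100 bpm: 435.5 - 419.6 = +15.9 ms, or 457.3 - 440.6 = +16.7 ms.
- 100 to 100 bpm: 0 ms.
- 100 to 80 bpm: -15.9 or -16.7 ms.

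**Masking.** Suppose QTcF is 420 ms at a baseline rate of 100 bpm, so QTcB is 457.3 ms. If the rate later falls to 80 bpm, QTcB stays at 457.3 ms when QTcF has become 457.3/1.0491 = 435.9 ms. A rise of 15.9 ms in QTcF would then show as no change in QTcB.

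**Feasibility.** Inverting the ratio, QTcF = QTcB x (60/HR)^(1/6). Both inputs are among the measurements named in SAP 3.5.5, so QTcF can be obtained even if it was not captured separately.

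**The case against.** The strongest objection is that nothing in the documents shows these patients to be tachycardic. A reader might infer that post-transplant patients will have fever and fast heart rates after infusion and so will show spurious QT prolongation. The documents do not support that, for four reasons.

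- They give no heart rates. Protocol 2.2.2.1 reports that infusions in the earlier study were well tolerated, with no cytokine release syndrome, and Protocol 10.6 calls that syndrome a theoretical concern for these cells. The infusion side effects in Protocol 2.3.2 include arrhythmia and hypotension but not fever or tachycardia.
- The direction is open. If rates are high early after transplant and settle later, the change in QTcB goes down; if rates are stable, the artefact cancels.
- SAP 3.5.5 tabulates no prolongation categories, so there are no counts to inflate.
- The arithmetic shows that the formulas disagree. The documents do not say which is nearer the truth in this population.

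All of this stands and limits the point.

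Three further objections carry less weight. First, all ECG parameters are to be listed by patient, and SAP 3.5.4 summarises pulse rate with change from baseline. But the SAP's list of ECG measurements contains only QTcB, a listing is not a summary, and pulse in a separate table is not paired with the ECG reading.

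Second, QTcF may not be in the database. Protocol 8.4.3 describes what the machine measures, and SAP 2.3.3 and 2.3.4 record that some other planned data were not collected in Phase 2. This is a fair caution, but the derivation above answers it.

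Third, the stakes are low. QTc is neither an adverse event of special interest (SAP 3.5.2) nor a named criterion for halting the study (Protocol 9.5.1.2). That is correct, and it sets the priority of the point without removing it.

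**Conclusion.** The point holds as a minor gap in the safety analysis. The protocol has both corrections measured and promises ECG summaries without restriction; the SAP summarises QTcB alone and gives no reason. QTcB exceeds QTcF at any rate above 60 bpm and falls below it at lower rates. Under the assumed QTcF, the gap is about 20 ms at 80 bpm and 36 to 37 ms at 100 bpm, and a 20 bpm change between those rates moves the change from baseline by about 16 to 17 ms in either direction.

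These sizes rest on assumed heart rates and QTcF values; the size and direction in this cohort cannot be known from the documents. Any effect would be confined to descriptive means and changes. It matters mainly because a single-arm cohort has no control against which to judge it.

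**What to change.** In SAP 3.5.5, add descriptive statistics and change from baseline for QTcF and for ECG heart rate, and keep QTcB alongside. Use QTcF as captured or, if it was not captured, derive it as QTcB x (60/HR)^(1/6) from the same ECG and state this in the section. If the sponsor prefers QTcB alone, the SAP should say why.

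SAP section 1 says that data were collected under Amendment 2 but that the analysis is based on Amendment 4, so the sponsor should confirm that the later amendment keeps both corrections.

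The cost is a few extra table rows and, at most, one simple derived variable. No new data are needed. SAP section 1 has the plan finalised before the Phase 2 database lock, so the change belongs before that point; if made later, the same section requires it to be documented in the clinical study report.
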